4. PROTOCOL COORDINATION, FUNDING, MODE

Regulatory Sponsor:

DF/HCC Investigator Cancer Imaging

Funding/Support (check all that apply):

Industry: Siemens

Primary Disease Group: Cancer Imaging

Federal Organization:

Grant #:

Internal Funding:

Non-Federal:

Other:

CTEP Study: No

Protocol Involves (check all that apply as listed in the protocol document, even if not part of the research but is mandated by the protocol document):

Chemotherapy

Hormone Therapy

Medical Record Review

Immunotherapy

Vaccine

Questionnaires/Surveys/Interviews

Surgery

Data Repository

Radiological Exams

Bone Marrow/Stem Cell Transplant

Exercise/Physical Therapy

Required Biopsy Study

Cell Based Therapy

Genetic Studies

Human Embryonic Stem Cell

Gene Transfer (use of recombinant DNA)

Human Material Banking

Quality of Life

Radiation Therapy

Human Material Collection

Other: Radiotracer administration for PET scans during routine Interventional Radiology Tumor Ablation procedure

5. SUBJECT POPULATION (also applies to medical record review and specimen collection studies)

Total Study-Wide Enrollment Goal: 75

Greater than 25% of the overall study accrual will be at DF/HCC: Yes No

Total DF/HCC Estimated Enrollment Goal: 75

Adult Age Range: 18+

Pediatric Age Range: N/A

Will all subjects be recruited from pediatric clinics? Yes No

If enrolling both adults and pediatric subjects, anticipated percent of pediatric subjects: N/A

Retrospective Medical Record Reviews only (Please provide date range): from to

6. DF/HCC PARTICIPANTS UNDER DFCI IRB (check all that apply)

Beth Israel Deaconess Medical Center (BIDMC)

Boston Children's Hospital (BCH)

Brigham and Women's Hospital (BWH)

Dana-Farber Cancer Institute (DFCI)

Massachusetts General Hospital (MGH)

Beth Israel Deaconess Medical Center – Needham (BIDMC-Needham)

Dana-Farber/New Hampshire Oncology-Hematology (DFCI @ NHOH)

Dana-Farber at Steward St. Elizabeth's Medical Center (DFCI @ SEMC)

Dana-Farber at Milford Regional Cancer Center (DFCI @ MRCC)

Mass General/North Shore Cancer Center (MGH @ NSCC)

Mass General at Emerson Hospital – Bethke (MGH @ EH)

DF/BWCC in Clinical Affiliation with South Shore Hospital (DFCI @ SSH)

7. NON-DF/HCC PARTICIPANTS UNDER DFCI IRB (check all that apply)

Cape Cod Healthcare (CCH)

Lowell General Hospital (LGH)

New Hampshire Oncology-Hematology-P.A. (NHOH)

Newton-Wellesley Hospital (NWH)

Dana-Farber/Faulkner Hospital (FH)

New England Cancer Specialists (NECS)

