8. DF/HCC INITIATED STUDIES ONLY - INSTITUTIONAL PARTICIPANTS UNDER OTHER IRB (N/A:)

DF/HCC Multi-Center Protocols: (list institution/location)

DF/PCC Network Affiliates: (list institution/location)

Protocol Number: 13-464

Approval Date: 11/26/13 (IRB meeting date when protocol/consent approved or conditionally approved)

Activation Date: 01/22/14 (Date when protocol open to patient entry)

Approval signatures are on file in the Office for Human Research Studies, [contact].

Date Posted	Revised Sections	IRB Approval Date	OHRS Version Date
02/04/14	Consent Form replaced due to Amendment #1	02/03/14	02/04/14
02/25/14	Correction: Consent Form replaced due to incorrect version previously provided (missing signature box)	02/03/14	02/04/14
06/17/14	Protocol replaced due to Amendment #2	06/11/14	N/A
11/26/14	ON HOLD: All research must stop due to lapsed Continuing Review. Study expired 11/26/14	N/A	N/A
04/27/15	Protocol, Consent Form and Front Sheet replaced due to Amendment #3	03/31/15	04/27/15
04/27/15	On HOLD removed; Study renewal/ Consent Form footer replaced due to Continuing Review #1	04/02/15	N/A
04/28/15	Temporary closed to new accrual: administrative hold by DMSC as of 4/28/2015. Questions regarding the temporary hold can be directed to the DSMC (via [name] in QACT)	n/a	n/a
05/29/15	Re-open to accrual – due to Amendment #4	05/18/15	N/A
06/18/15	Temporary closed to new accrual: administrative hold per the IRB on 06/04/15 (OE #4).	n/a	n/a
Date Posted	Revised Sections	IRB Approval Date	OnCore Version Date
09/29/15	Study Re-Opened due to Amendment #5	08/28/15	N/A
11/17/15	Consent Form replaced due to Amendment #6	11/09/15	11/13/15
03/24/16	Consent Form replaced due to Amendment #7	02/29/16	03/07/16
03/31/16	Study renewal / Consent Form footer replaced due to Continuing Review #2	03/24/16	03/31/16
Date Posted	Revised Sections	Approved Date	Version Date (OnCore)
12/12/16	Arm 2 of study opened; Arm 1 now closed to accrual: Protocol, Eligibility Checklist and Front Sheet replaced; Arm 2 Consent Form added due to Amendment #8	10/04/16	12/12/16
Date Posted	Revised Sections	Approved Date	Version Date (OnCore)
03/22/2017	Study renewal/ Consent Form footers replaced due to Continuing Review #3	03/16/2017	03/22/2017
03/15/2018	Study renewal/Consent Form footers replaced per Continuing Review #4	03/01/2018	03/15/2018
03/26/2018	Permanent Closure to New Accrual: due to Funding (effective date: 03/09/2018; Amendment #9)	n/a	n/a

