14. STATISTICAL CONSIDERATIONS

14.1 Study Design/Endpoints

Arm 2: Study design/endpoints are identical for Arms 1 & 2.

In this study of patients with liver lesions, it is expected that roughly two-thirds of patients will have FDG-avid tumors, one-third of patients will have non FDG-avid tumors, and although it is possible for a patient to have both types of tumor, that is considered rare. For sample size and power considerations we therefore conservatively assume that patients will have one type of tumor or the other and therefore target a sample size of 100 patients per arm, allowing for the potential for renal insufficiency in up to 25% of all patients (described in more detail below). Also, as the techniques focus on analysis by tumor and it is estimated that 70% of patients will have only a single lesion, the sample size considerations will focus on enrolling *patients* rather than *tumors*. Multiple tumors per patient, when they occur, will be treated and assessed in the statistical analysis, with appropriate adjustment for clustering of tumors within a patient to account for correlation of responses within a patient. Sample size considerations, however, focus on enrollment of patients. The study design and endpoints are identical for Arm 1 and Arm 2.

Primary Objectives:

1. Among FDG-avid liver tumors, comparison of imaging techniques will be done on paired tumor samples using McNemar's test, focusing on discordant pairs (AP-PET-1 adequate/CECT inadequate and AP-PET-1 inadequate/CECT adequate). For these comparisons it is expected that the rate of discordance will be high (near 60% of all pairs) and that differential in discordance will be large (difference between discordant pairs on the order of 50% or higher). In addition to comparing discordant pairs, there is interest in being able to precisely estimate the visibility rates under each imaging modality. With 50 paired samples in the FDG-avid liver tumor ablation group in each arm, visibility of the entire ablation margin can be estimated with a 95% binomial confidence interval that should be no wider than 24 percentage points (+/- 12%) in the expected range of visibility of each modality (80% for AP-PET and 20% for CECT). This sample size will provide greater than 90% power for McNemar's test using a 5% type I error given the assumptions above about discordance.

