14.2 Sample Size/Accrual Rate

Target enrollment for each arm of the study is 100 patients. Each patient will be followed for 12 months after their study procedure(s). An accrual rate of 3-6 subjects/month is anticipated. Enrollment of 200 total patients is expected to be completed within 3-4 years.

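### The front sheet sets a study-wide enrolment goal of 75, while Section 14 plans 100 per arm and 200 in total; separately, Objective 3 counts 75 FDG-avid cases per arm where the design yields 67

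*Combined protocol and SAP*

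**What the plan says.** Item 5 of the front sheet gives two enrolment figures, "Total Study-Wide Enrollment Goal: 75" and "Total DF/HCC Estimated Enrollment Goal: 75".

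Section 14.1 tells the reader to "target a sample size of 100 patients per arm". Section 14.2 agrees, "Target enrollment for each arm of the study is 100 patients", and gives the sum for both arms, "Enrollment of 200 total patients". The unit is the patient, not the tumour: "Sample size considerations, however, focus on enrollment of patients".

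Section 14.1 builds the 100 from 67 FDG-avid patients (Objective 1) and 33 non-FDG-avid patients (Objective 4), after allowing for 25% of pairs lost to renal insufficiency. Objective 3 then bases its precision on 75 FDG-avid cases per arm, about 71 of them nominally adequate. Its counterpart for non-avid tumours, Objective 5, uses 33.

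The front sheet's revision history has two relevant entries. The December 2016 entry reads "Arm 2 of study opened; Arm 1 now closed to accrual: Protocol, Eligibility Checklist and Front Sheet replaced", so the arms ran one after the other and both documents were reissued together. The March 2018 entry reads "Permanent Closure to New Accrual: due to Funding" and mentions no revised target.

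**The concern.** A study-wide goal of 75 is below the target for a single arm, let alone for two. As the front sheet was reissued together with the protocol when Arm 2 opened, it cannot be set aside as a leftover from a one-arm study.

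Accrual ended early for lack of funding, so achieved enrolment will have to be judged against a plan. The documents offer 75, 100 per arm and 200 in total without choosing. The choice matters because some precision statements for the primary objectives hold only at Section 14's number.

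The Objective 3 count is a second, independent inconsistency. It puts more FDG-avid cases in an arm than the planned enrolment is expected to supply.

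**Working it through.** **Inputs (all Section 14.1).** FDG-avid share two-thirds; 50 FDG-avid and 25 non-avid pairs per arm; 25% of pairs lost to renal insufficiency; discordance 60% with a difference of 50 points (Objective 1) and 70% with 60 points (Objective 4); expected visibility 80% for AP-PET and 20% for CECT; type I error 5%. Sidedness is not stated, so two-sided is assumed.

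**Formulas.** Inflation: n/(1 − loss). Exact (Clopper-Pearson) limits: the 0.025 quantile of Beta(x, n−x+1) and the 0.975 quantile of Beta(x+1, n−x). Wald width: 2 × 1.96 × √(p(1−p)/n). Wilson width: 2z/(1+z²/n) × √(p(1−p)/n + z²/(4n²)), with z = 1.96. McNemar cell probabilities: (discordance ± difference)/2, that is 0.55/0.05 for Objective 1 and 0.65/0.05 for Objective 4. All widths are in percentage points.

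**1. The plan's own figures reproduce.** 50/0.75 = 66.7, stated as 67. 25/0.75 = 33.3, stated as 33. 67 + 33 = 100 per arm; × 2 = 200.

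| Quantity | Count | Exact width | Stated |
|---|---|---|---|
| Objective 1 visibility | 40/50 | 23.7 | 24 |
| Objective 2 visibility near 90% | 45/50 | 18.5 | 19 |
| Objective 3 adequacy | 64/71 | 15.2 | 16 |
| Objective 3 concordance | 37/75 | 23.6 | 24 |
| Objective 4 visibility | 20/25 | 33.9 | 34 |
| Objective 5 concordance | 16/33 | 35.7 | 36 |

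McNemar power (exact / uncorrected) is 0.999 / 1.000 at 50 pairs and 0.984 / 0.992 at 25 pairs. The stated bounds fit the exact method best, although the plan names no method.

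**2. If 75 governs, most favourable reading: all 75 in one arm.** This gives 75 × 2/3 = 50 FDG-avid and 25 non-avid patients. At 25% loss the pairs are 37.5 and 18.75.

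Met:
- McNemar power: Objective 1 0.993 (37 pairs); Objective 4 0.911 to 0.928 (18 to 19 pairs), exact.
- AP-PET-1 visibility on all patients: 23.7 against 24, and 33.9 against 34.

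Missed whatever the renal loss, because these objectives do not need contrast (concordance at the plan's conservative 50%):

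| Quantity | Count | Exact | Wald | Wilson | Stated |
|---|---|---|---|---|---|
| Objective 3 concordance | 25/50 | 28.9 | 27.7 | 26.7 | 24 |
| Objective 5 concordance | 12/25 | 40.9 | 39.2 | 36.5 | 36 |

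Missed at the plan's 25% renal loss:

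| Quantity | Pairs | Exact | Wald | Wilson | Stated |
|---|---|---|---|---|---|
| Objective 1, CECT or paired | 37–38 | 26.6–28.4 | 24.7–26.5 | 24.2–25.8 | 24 |
| Objective 2, PET/CECT near 90% | 37–38 | 21.9–22.4 | 19.5–20.0 | 20.0–20.4 | 19 |
| Objective 4, CECT or paired | 18–19 | 37.8–41.2 | 34.4–38.4 | 33.4–36.2 | 34 |

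At zero loss the Objective 1 and 4 widths are met (23.7 and 33.9). At 10% loss (45 and 22 to 23 pairs) the answer depends on method and rounding. Objective 1 is 25.0 exact, 23.4 Wald and 22.9 Wilson; Objective 4 is 33.8 to 37.5 exact, 31.0 to 35.0 Wald and 30.2 to 33.3 Wilson.

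**3. Illustration only: 75 split evenly.** The documents do not state this allocation. Each arm would have 25 FDG-avid and 12.5 non-avid patients, hence about 19 and 9 pairs. Power (exact to uncorrected) falls to 0.83–0.89 for Objective 1 and 0.45–0.68 for Objective 4. Even the AP-PET-1 widths are then missed: 33.9 against 24 (20/25) and 46.3 to 48.8 against 34 (10/12, 10/13).

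**4. Objective 3 at the planned enrolment.** 100 × 2/3 = 67, not 75. With Objective 5's 33 cases, 75 + 33 = 108 per arm against 100. Nominally adequate: 0.95 × 75 = 71 as stated, but 0.95 × 67 = 64. At 67 cases:
- Concordance (33/67): 24.9 exact, 23.9 Wald, 23.3 Wilson, against 24.
- Adequacy (57/64 or 58/64): 16.7 or 15.8 exact, 14.3 to 15.5 by Wald or Wilson, against 16.

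**The case against.** **Section 14 clearly governs, so the front sheet is only an administrative slip.** Section 14 states 100 per arm twice, derives it and totals it. That makes 200 the likelier intention, but it does not remove the contradiction in two documents reissued together. If the field is stale, it needs correcting.

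**75 may be the 50 + 25 pairs, or the result of early closure.** The documents make no such link. Those pairs are per arm, while the front sheet says study-wide. The early-closure provision depends on the renal-insufficiency rate; it would reach 75 patients in one arm only at zero loss, and it does not address the concordance objectives.

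**The consequences are hypothetical and partly depend on the method.** This stands in part. Power survives in the one-arm reading, the Objective 4 widths straddle the bound by Wilson, the Objective 2 miss is only about 0.5 to 1.4 points by Wald or Wilson, and the even split is an assumption. At a true concordance of 80%, the top of the plan's range, 50 and 25 cases would give 23.7 and 33.9, inside 24 and 36. The concordance misses therefore rest on the 50% rate, but that is the rate on which the plan bases its own bounds.

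**Objective 3's cases may be tumours.** The analysis is by tumour, and about 30% of patients are expected to have more than one, so 67 patients could supply 75 tumours and tumour-level intervals could be somewhat narrower. But sizing is in patients, and Objective 5 uses the patient count. The tumour mix in Section 1.1 also gives at least 0.70 + 0.30 + 0.30 + 0.20 = 1.5 tumours per patient (taking four for more than three), about 100 from 67 patients rather than 75.

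**Accrual has closed.** True, so the effect is on reporting and not on conduct.

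**Conclusion.** The concern holds. The enrolment target contradicts itself (75 against 200, and against 100 for one arm), and the supplied text does not resolve it. Section 14's derivation of 100 per arm is otherwise correct.

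The size depends on which figure governs. At 200, only the front sheet and the Objective 3 count are wrong. At 75, even if all patients were in one arm, the concordance bounds for Objectives 3 and 5 fail by all three interval methods: by 2.7 to 4.9 points and by 0.5 to 4.9 points. Several paired-visibility bounds also fail at the plan's 25% renal loss. These results assume one tumour pair per patient, the two-thirds FDG-avid share and a two-sided 5% test.

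The Objective 3 slip alone is small: seven fewer nominally adequate cases, and a stated concordance width missed by 0.9 points by the exact method and met by the other two. The point should be fixed, chiefly for the sake of the enrolment target.

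**What to change.** State the governing enrolment figure.

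- **If it is 200:** correct the front sheet to 100 per arm and 200 in total.
- **If it is 75:** state the allocation between arms, and restate the pairs, widths and power in Sections 14.1 and 14.2 for that number.
- **In either case:** recompute Objective 3 from the FDG-avid number that enrolment yields (67 cases and about 64 nominally adequate at 100 per arm), and name the interval method.
- **In the report:** because accrual has closed, give the governing planned figure beside the pairs and cases actually obtained in each arm.

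The cost is one front-sheet field or some wording in Section 14, with no extra patients. The stated precision for Objective 3 becomes slightly less favourable, as do other widths if 75 governs.

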8. DF/HCC INITIATED STUDIES ONLY - INSTITUTIONAL PARTICIPANTS UNDER OTHER IRB (N/A:)

DF/HCC Multi-Center Protocols: (list institution/location)

DF/PCC Network Affiliates: (list institution/location)

Protocol Number: 13-464

Approval Date: 11/26/13 (IRB meeting date when protocol/consent approved or conditionally approved)

Activation Date: 01/22/14 (Date when protocol open to patient entry)

Approval signatures are on file in the Office for Human Research Studies, [contact].

Date Posted	Revised Sections	IRB Approval Date	OHRS Version Date
02/04/14	Consent Form replaced due to Amendment #1	02/03/14	02/04/14
02/25/14	Correction: Consent Form replaced due to incorrect version previously provided (missing signature box)	02/03/14	02/04/14
06/17/14	Protocol replaced due to Amendment #2	06/11/14	N/A
11/26/14	ON HOLD: All research must stop due to lapsed Continuing Review. Study expired 11/26/14	N/A	N/A
04/27/15	Protocol, Consent Form and Front Sheet replaced due to Amendment #3	03/31/15	04/27/15
04/27/15	On HOLD removed; Study renewal/ Consent Form footer replaced due to Continuing Review #1	04/02/15	N/A
04/28/15	Temporary closed to new accrual: administrative hold by DMSC as of 4/28/2015. Questions regarding the temporary hold can be directed to the DSMC (via [name] in QACT)	n/a	n/a
05/29/15	Re-open to accrual – due to Amendment #4	05/18/15	N/A
06/18/15	Temporary closed to new accrual: administrative hold per the IRB on 06/04/15 (OE #4).	n/a	n/a
Date Posted	Revised Sections	IRB Approval Date	OnCore Version Date
09/29/15	Study Re-Opened due to Amendment #5	08/28/15	N/A
11/17/15	Consent Form replaced due to Amendment #6	11/09/15	11/13/15
03/24/16	Consent Form replaced due to Amendment #7	02/29/16	03/07/16
03/31/16	Study renewal / Consent Form footer replaced due to Continuing Review #2	03/24/16	03/31/16
Date Posted	Revised Sections	Approved Date	Version Date (OnCore)
12/12/16	Arm 2 of study opened; Arm 1 now closed to accrual: Protocol, Eligibility Checklist and Front Sheet replaced; Arm 2 Consent Form added due to Amendment #8	10/04/16	12/12/16
Date Posted	Revised Sections	Approved Date	Version Date (OnCore)
03/22/2017	Study renewal/ Consent Form footers replaced due to Continuing Review #3	03/16/2017	03/22/2017
03/15/2018	Study renewal/Consent Form footers replaced per Continuing Review #4	03/01/2018	03/15/2018
03/26/2018	Permanent Closure to New Accrual: due to Funding (effective date: 03/09/2018; Amendment #9)	n/a	n/a

1. OBJECTIVES

1.1 Study Design - Abstract

Arm 2: This study has two arms. Arm 1 is the protocol as written below using Ammonia perfusion PET to assess ablation results of standard FDG PET/CT-guided liver tumor ablations. Arm 2 is the identical protocol, but substitutes the radiopharmaceutical FDG for Ammonia to assess ablation results of standard FDG PET/CT-guided liver tumor ablations. Arm 2 will not include the option of performing a second intra-procedural perfusion PET scan. FDG is FDA-approved for oncologic imaging as in this study. No IND or IND exemption is required. The protocol is identical in all other respects. All protocol comments pertaining to Arm 2 will be placed in new paragraphs beginning with “Arm 2:” in bold letters. Throughout the protocol, Arm 2 simply substitutes FDG for N-13 ammonia. In Arm 2, All AP-PET scans (which are the only research intervention of the study) are performed using FDG instead of N-13 ammonia.

Arm 1 and Arm 2 are independent and no randomization or enrollment criteria for one arm or the other are defined.

[figure not shown]
The purpose of this study is to evaluate a novel imaging technique for intra-procedural assessment, also known as monitoring, of image-guided percutaneous liver tumor microwave or cryoablation (thermal ablation) procedures. Monitoring assures that the tumor is being ablated completely (and nearby critical structures left unharmed) by allowing the interventionalist to view ablative changes and make intra-procedural adjustments to the location of the ablation applicators, the number of overlapping ablation treatments, or the duration of ablation applications. As a result, improved monitoring has the potential to improve patient outcomes. We will assess a novel method for monitoring ¹⁸F-fluorodeoxyglucose (FDG) Positron Emission Tomography/Computed Tomography (PET/CT)-guided liver tumor ablations: intra-procedural ¹³N-ammonia perfusion PET (AP-PET). N-13 ammonia is FDA-approved for cardiac perfusion imaging, but will be used in this study for the off-label indication of imaging perfusion of the liver. The standard dose and IV route of administration will be employed. We will compare this method of assessing immediate technical success of ablation procedures to standard assessments using intra-procedural contrast-enhanced CT (CECT). We will also compare final intra-procedural ammonia perfusion PET to gold standard 24-hour magnetic resonance imaging (MRI) or CT for predicting longer term technique effectiveness as demonstrated on routine MRI (or if MRI is not possible, on CT) obtained at a minimum of three to 12 months after the procedure.

This study will evaluate if AP-PET can be used intra-procedurally during FDG PET/CT-guided ablation procedures to identify regions of the ablation zone that do not adequately treat the tumor. The ablation zone is the volume of tissue destroyed by the ablation treatment. Adequate ablation treatment of tumor is generally defined by a minimum ablation margin of 5-10 mm. The ablation margin refers to the rim of normal tissue beyond the tumor included within the ablation zone in order to assure that even microscopic tumor

CONFIDENTIAL

This document is confidential. Do not disclose or use except as authorized.

extensions beyond the visible tumor are fully destroyed.

The ablation zone includes the ablated tumor and a cuff of ablated surrounding normal liver (ablation margin).

The ability to directly visualize and assess the ablation margin requires visibility of both the tumor and the boundaries of the ablation zone. Unfortunately, tumor visibility using CT or US is often lost or diminished immediately following thermal ablation. On the other hand, the entire ablation zone is generally visible as a region of decreased or absent enhancement on CECT scans obtained following the ablation. The ablation zone is usually poorly defined on US imaging obtained after ablation. Because of these limitations of CT and US, the ablation margin is usually estimated using side-by-side comparisons of the size and shape of the ablation zone as depicted on intra-procedural post-ablation CECT with the pre-procedural MRI or CT appearance and location of the tumor. Alternatively, retrospective software fusion of the post-ablation CECT with pre-procedural MRI or CT can be used. Unfortunately, these standard approaches often do not allow for confident point-by-point assessment of the entire circumference of the ablation margin. These limitations of our standard imaging techniques for the intra-procedural assessment or monitoring of thermal ablation procedures in the liver underscore the need for identifying more robust techniques. This study explores a novel imaging technique with the potential to improve our intra-procedural assessment of ablation results and, in turn, patient outcomes.

Adult patients referred to our Tumor Ablation Clinic for image-guided percutaneous ablation of liver tumors will be considered for enrollment. Patients who meet our standard clinical criteria for image-guided liver tumor ablations will be offered the opportunity to enroll in this prospective study. Standard clinical criteria include a known primary or metastatic malignancy of the liver for which local therapies are being considered. These may include tumors that are unresectable for any reason or tumors in patients who have comorbidities precluding surgery. Liver tumor ablations are also performed to reduce the

CONFIDENTIAL

This document is confidential. Do not disclose or use except as authorized.

6/9/2014

tumor burden in patients with advanced disease or to palliate symptoms such as pain. Liver tumor ablation may serve as a bridge to liver transplantation in patients with hepatocellular carcinoma. Ablation may be an option for patients who do not wish to undergo open surgical procedures. It is expected that approximately 2/3 of the tumors will prove to be FDG-avid and 1/3 non-FDG-avid. It is anticipated that we will ablate a single liver tumor per procedure in approximately 70% of patients, two liver tumors in 15% of patients, three liver tumors in 10% of patients, and more than three tumors in 5% of patients, based on our recent practice experience. Patients will be excluded for uncorrectable coagulopathy or severe inter-current illness. Tumor ablation procedures will be performed as they are routinely performed by our team in clinical practice using FDG PET/CT and possible supplemental US guidance. Targeting can be accomplished based on tumor visibility on any one or more of these imaging modalities (US, PET, or CT). FDG-avidity is not essential for the targeting of tumors. Patients enrolled in this study will receive ablation treatments that will not be compromised by the research portions of the procedures.

The ablation will be planned and the ablation applicators inserted percutaneously using routine FDG PET/CT and possible supplemental US guidance. The ablation will then be performed using current protocols with either microwave ablation or cryoablation devices. Microwave ablation and cryoablation devices offer complimentary advantages that enable us to safely and effectively treat many liver tumors. Cryoablation may be better tolerated and less painful when ablating liver tumors close to the liver capsule or diaphragm. The iceball created during cryoablation is usually well visualized during the ablation, which can offer safety advantages when ablating near critical structures. Microwave ablation has fewer tendencies to induce thrombocytopenia or myoglobinemia than cryoablation, which can be an advantage in patients with baseline thrombocytopenia or renal insufficiency. Microwave ablation is better able to overcome vascular heat-sink phenomena that can limit the ablation of tumor cells abutting large blood vessels. Our standard practice is to choose the most appropriate ablation technology based on the individual patient's specific circumstances. Radiofrequency ablation is not included in this protocol, as microwave ablation has almost completely replaced the use of radiofrequency ablation in our practice.

[figure not shown]
When the initial ablation is completed, intra-procedural AP-PET-1 (research scan #1) will be performed and the findings recorded. Specifically, the ablation margin separating the FDG-avid tumor from the normal ammonia-perfused liver will be assessed for visibility and thickness along the entire circumference. Patients with adequate renal function (EGFR >60) will then undergo intra-procedural contrast-enhanced CT, as is now performed in routine clinical practice to monitor initial results. Non-contrast CT will be used in cases of inadequate renal function or contrast allergy. If no additional overlapping ablation applications are deemed necessary or appropriate based on routine CT (Pathway 1), the procedure will be concluded at this point. AP-PET information may be used to aid the margin assessment if CT is inconclusive. Note that routine CT will always be used to determine the safety of additional overlapping ablation, per routine clinical practice. This is because proximity of ablation devices to critical structures can only be imaged with CT and not with PET. The patient will then undergo routine 24-hour post-procedure liver MRI

CONFIDENTIAL

This document is confidential. Do not disclose or use except as authorized.

or CT. If the CT scan suggests an inadequate ablation margin of less than 5-10 mm at any portion of the tumor surface, additional ablations will be applied to the under-treated areas (Pathway 2), if deemed safe and appropriate based on standard clinical practice. Then, AP-PET-2 will be repeated (research scan #2). Not more than two AP-PET scans will be performed during the entire procedure. The AP-PET scan(s), illustrated schematically below, constitute the only research component of the protocol.

Arm 2: Arm 2 will not include the option of AP-PET 2 (research scan #2) due to the longer half-life of FDG.

The devascularized ablation zone contains trapped high tumor FDG activity and low ablation margin FDG activity, whereas normal liver is perfused with high activity ¹³N-ammonia. The relatively photopenic ring around the tumor confirms the presence of an adequate ablation margin.

For patients with FDG-avid tumors, visibility rates of the entire ablation margin using AP-PET-1 will be compared to the visibility rates of the entire ablation margin using the intra-procedural CECT scan. Visibility rates using AP-PET-1 will also be compared to the visibility rates using the intra-procedural CECT scan fused to FDG PET (FDG PET/CECT). The concordance rates of the final intra-procedural AP-PET (research scan #1 or #2) with gold standard 24-hour post-procedure MRI or CT will be determined.

For those patients with non-FDG-avid tumors, retrospective software fusion of AP-PET-1 with pre-procedural MRI or CT will be used to assess visibility rates of the ablation margin and will be compared with visibility rates of the ablation margin using retrospective fusion of the intra-procedural CECT and pre-procedural MRI or CT. Similarly, in patients with non-FDG-avid tumors the concordance rate of final intra-procedural AP-PET (research scan #1 or #2) fused to pre-procedural MRI or CT, with gold standard 24-hour post-procedure MRI or CT will be determined. The analysis of AP-PET utility in patients with non-FDG-avid tumors is a secondary objective of this study, but is nevertheless of interest, as AP-PET may prove valuable in these patients who cannot receive IV contrast or

CONFIDENTIAL

This document is confidential. Do not disclose or use except as authorized.

potentially as a superior assessment for patients who can receive IV contrast. Prediction of longer term technique effectiveness rates (local recurrence rates) based on blinded retrospective reads will be compared for the final intra-procedural AP-PET scan and 24-hour MRI or CT, using local tumor progression as assessed on routine follow-up MRI or CT scans performed at least 3 to 12 months after the ablation procedure as the gold standard. Liver contrast-enhanced MRI is preferred for routine 24-hour follow-up imaging, however, contrast-enhanced CT may be substituted if the patient cannot undergo MRI due to contraindications such as incompatible implanted devices.

The results of this study are expected to show that AP-PET can be used to reveal areas of ablation under-treatment or areas of optimal treatment that are not consistently identified with contrast-enhanced CT alone. Better intra-procedural assessment of tumor ablation results has the potential to improve image-guided tumor ablation technical success and effectiveness rates.

